9.3 Prohibited Medications

Medications that are prohibited in this study (Screening Period through the Safety Follow-up Visit) are shown in Table 9-1. VX-152, VX-661, and IVA are metabolized extensively via cytochrome P450 (CYP) 3A4. VX-152 is also metabolized by CYP2C9. Therefore, the use of moderate and strong inducers of CYP3A or CYP2C9 and strong and moderate inhibitors of CYP3A, which have the potential to alter the exposure of VX-152, VX-661, or IVA, will be restricted in this study. VX-152 was shown in vitro to be an inhibitor of the hepatic transporters organic anion transporting polypeptide 1B1 (OATP1B1) and 1B3 (OATP1B3). Therefore, sensitive substrates of OATP1B1/1B3, such as HMG Co-A Reductase Inhibitors (i.e., “statins”), are also restricted during the study.

A non-exhaustive list of study prohibitions and cautions for medication will be provided in the Study Reference Manual.

Table 9-1 Study Restrictions

Medication	Timing of Restriction	
	Start of Restriction	End of Restriction
Moderate and strong CYP3A or CYP2C9 inducers	None allowed within 14 days before the first dose of the study drug on Day 1 (Part 1) or Day -28 (Part 2)	None allowed through the Safety Follow-up Visit
Moderate and strong CYP3A inhibitors (except ciprofloxacin)	None allowed within 14 days before the first dose of the study drug on Day 1 (Part 1) or Day -28 (Part 2)	None allowed through the Safety Follow-up Visit
Sensitive OATP1B1/1B3 substrates	None allowed within 14 days before the first dose of VX-152 or placebo on Day 1	None allowed until after last dose of VX-152 or placebo
Commercially available CFTR modulators (e.g., Kalydeco, Orkambi)	Part 1: None allowed within 14 days before screening Part 2: None allowed from the start of the Run-in Period	Part 1: None allowed through the Safety Follow-up Visit Part 2: None allowed through the end of the Washout Period

Note: The use of restricted medication by subjects with medical needs will be addressed on a case-by-case basis with the medical monitor.

9.4 Prior and Concomitant Medications

Information regarding all prior and concomitant medications, including the subject's CF medications, other medications, and herbal and naturopathic remedies administered from 28 days before the Screening Period through the Safety Follow-up Visit, if applicable, will be recorded in each subject's source documents. For subjects who are screened but are not subsequently randomized in the study, details of prior medication will only be documented in the subjects' source documents.

- Subjects must remain on a stable medication (and supplement) regimen for their CF from 28 days before Day 1 through the Safety Follow-up Visit. Stable medication regimen is defined as the current medication regimen for CF that subjects have been following for at least 28 days before Day 1. Subjects must not initiate long-term treatment with new medication from 28 days before Day 1 through the Safety Follow-up Visit unless discussed and approved by the medical monitor. Guidelines for stable medication regimens for CF are as follows:
 - Subjects who are taking daily inhaled tobramycin or other chronically inhaled antibiotics should remain on that regimen throughout the study.
 - Subjects who cycle onto and off an inhaled antibiotic should continue on their prior schedule. The timing of the first dose of study drug on Day 1 should be synchronized as closely as possible (and not more than ± 3 days) to the first day in the cycle onto the inhaled antibiotic.
 - Subjects who alternate between 2 different inhaled antibiotics should remain on the same cycling schedule during the study. The timing of the first dose of study drug on Day 1 should be synchronized as closely as possible (and not more than ± 3 days) to the first day in the cycle onto 1 of the inhaled antibiotics.
- Subjects may receive doses of prednisone of up to 10 mg/day or equivalent (chronically) or prednisone 60 mg qd for up to 5 days without prior approval of the medical monitor.
- Information about bronchodilator use during the study will be collected and documented. Subjects who are using a bronchodilator must have their spirometry assessments performed according to the guidelines provided in [Section 11.6.1](#).

9.5 Removal of Subjects

Subjects may withdraw from the study at any time at their own request. Subjects may be withdrawn from study drug treatment at any time at the discretion of the investigator or Vertex for safety, behavior, noncompliance with study procedures, or administrative reasons. If a subject has been withdrawn from study drug treatment, the subject will continue to be followed, provided the subject has not withdrawn consent.

Subjects who have been randomized and whose screening *CFTR* genotype does not confirm study eligibility must be discontinued from the study, even if a previous *CFTR* genotype laboratory report was used to establish eligibility.

If a subject does not return for a scheduled visit, reasonable effort will be made to contact the subject. In any circumstance, reasonable effort will be made to document subject outcome.

The investigator will inquire about the reason for withdrawal, request that the subject return all unused investigational product(s), request that the subject return for a Safety Follow-up Visit, if applicable (see [Section 8.1.6](#)), and follow up with the subject regarding any unresolved AEs.

If the subject withdraws consent for the study, no further evaluations will be performed and no additional data will be collected. Vertex may retain and continue to use any data collected before such withdrawal of consent.

9.6 Replacement of Subjects

Subjects who withdraw or are withdrawn before the first dose of study drug on Day 1 may be replaced.

Subjects who withdraw or are withdrawn for nonsafety reasons during the study drug treatment period may be replaced at Vertex's discretion.

10 STUDY DRUG ADMINISTRATION AND MANAGEMENT

Study drug refers to VX-152, VX-661/IVA, IVA, and their matching placebos.

10.1 Preparation and Dispensing

Study drug may be dispensed only under the supervision of the investigator or an authorized designee and only for administration to the study subjects.

10.2 Administration

Study drug will be administered orally. Subjects will receive the same number of tablets each day to maintain the blind. Additional information is provided in the Pharmacy Manual.

Study drug will be administered with a fat-containing meal or snack, such as a standard "CF" high-fat, high-calorie meal or snack or a standard meal, according to the following guidelines:

1. It is recommended that the dose be taken within 30 minutes of the start of the meal or snack.
2. Study drug will be administered q12h (\pm 2 hours). For each subject, all doses of study drugs will be taken at approximately the same time each day. For example, the morning dose could be taken at 08:00 every morning and the evening dose could be taken at 20:00 every evening throughout the study.
3. The date, amount taken, and time of study drug administration, including whether food was taken with each dose, will be recorded for the 2 doses before PK sample collection and the dose received on the morning of PK sample collection.
4. On days of scheduled visits, the morning dose of study drug will be administered at the site after predose assessments have been completed. The meal or snack will be provided by the site for the morning dose of study drug.

5. If a subject's scheduled visit is to occur in the afternoon, the following guidelines must be used:
 - If the dose in the clinic will be within 6 hours of the subject's scheduled morning dose, the subject should withhold their morning dose of study drug and the morning dose will be administered in the clinic.
 - If the dose in the clinic will be more than 6 hours after the subject's scheduled morning dose, the subject should take the morning dose at home and the evening dose will be administered in the clinic. In this event, all assessments will be collected relative to the evening dose.
6. For visits after the Day 1 Visit, subjects will be instructed to bring all used and unused study drug to the site; study drug will be dispensed at each visit, as appropriate.

10.2.1 Missed Doses

If a subject misses a dose and recalls the missed dose within 6 hours, the subject should take his/her dose with food. If more than 6 hours have elapsed after his/her usual dosing time, the subject should skip that dose and resume his/her normal schedule for the following dose. For example,

- if the morning dose of study drug should have been taken at approximately 08:00, and the subject remembers at 12:00 that he/she forgot to take his/her dose, he/she should take the dose with food as soon as possible.
- if the morning dose of study drug should have been taken at approximately 08:00, and more than 6 hours have elapsed beyond the scheduled dosing time (i.e., the time is past 14:00), the subject would resume dosing with the evening dose at approximately 20:00.

10.3 Method of Assigning Subjects to Treatment Groups

Approximately 12 subjects (Part 1 and Part 2, Cohort 1A) and approximately 24 subjects (Part 2, Cohort 2B) will be randomized in the ratio 3:1 to TC versus comparator in each cohort. An interactive web response system (IWRS) will be used to assign subjects to treatment. The randomization code list will be produced by Vertex Biostatistics or a qualified randomization vendor.

10.4 Study Drug Interruption and Stopping Rules

Subjects with new treatment-emergent ALT or AST elevations of $>3 \times \text{ULN}$, or total bilirubin $>2 \times \text{ULN}$, must be followed closely, including confirmatory testing performed by the central laboratory within 48 to 72 hours of the initial finding and subsequent close monitoring of ALT, AST, and bilirubin levels, as clinically indicated.

If a subject cannot return to the site for confirmatory testing, a local laboratory may be used. Local laboratory results must be reported immediately to the medical monitor, and the subject must have the tests repeated and sent to the central laboratory as soon as possible (ideally within 48 to 72 hours).

Study drug administration **must be interrupted** immediately (prior to confirmatory testing), and the medical monitor must be notified, if any of the following criteria are met:

- ALT or AST $>8 \times$ ULN
- ALT or AST $>5 \times$ ULN for more than 2 weeks
- ALT or AST $>3 \times$ ULN, in association with total bilirubin $>2 \times$ ULN and/or clinical jaundice
- Indirect bilirubin $>2 \times$ ULN (defined as ULN for total bilirubin minus ULN for direct bilirubin)

A thorough investigation of potential causes should be conducted, and the subject should be followed closely for clinical progression.

Study drug administration **must be discontinued**, if confirmatory testing results obtained after study drug interruption meet any of the following criteria:

- ALT or AST $>8 \times$ ULN
- ALT or AST $>5 \times$ ULN for more than 2 weeks
- ALT or AST $>3 \times$ ULN, in association with total bilirubin $>2 \times$ ULN and/or clinical jaundice
- Indirect bilirubin $>2 \times$ ULN (defined as ULN for total bilirubin minus ULN for direct bilirubin), in association with decreased haptoglobin

If an alternative, reversible cause of transaminase elevation and/or increased bilirubin or clinical jaundice has been identified, study drug administration may be resumed once transaminases or bilirubin return to baseline or are $\leq 2 \times$ ULN, whichever is higher. Approval of the medical monitor is required before resumption of study drug.

All subjects in whom treatment is discontinued for elevated transaminases and/or bilirubin should have these levels monitored closely until levels normalize or return to baseline.

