9.2 Exclusion Criteria

1. History of any comorbidity that, in the opinion of the investigator, might confound the results of the study or pose an additional risk in administering study drug to the subject.
2. History of cirrhosis with portal hypertension.

3. Risk factors for Torsade de Pointes, including but not limited to, history of any of the following: familial long QT syndrome, chronic hypokalemia, heart failure, left ventricular hypertrophy, chronic bradycardia, myocardial infarction, cardiomyopathy, history of arrhythmia (ventricular or atrial fibrillation), obesity, acute neurologic events (subarachnoid hemorrhage, intracranial hemorrhage, cerebrovascular accident, or intracranial trauma), or autonomic neuropathy.
4. History of hemolysis.
5. G6PD deficiency, defined as G6PD activity less than the lower limit of normal (LLN) or 70% of the mean of the LLN and the ULN, whichever is greater.
6. Any of the following abnormal laboratory values at screening:
 - Hemoglobin <10 g/dL
 - Total bilirubin $\geq 2 \times$ ULN
 - AST, ALT, gamma-glutamyl transpeptidase (GGT), or alkaline phosphatase (ALP) $\geq 3 \times$ ULN
 - Abnormal renal function defined as glomerular filtration rate ≤ 50 mL/min/1.73 m² (calculated by the Modification of Diet in Renal Disease Study Equation)^{10,11} for subjects ≥ 18 years of age
7. An acute upper or lower respiratory infection, pulmonary exacerbation, or changes in therapy (including antibiotics) for pulmonary disease within 28 days before the first dose of study drug (Day 1 for Part 1, Day -28 for Part 2).
8. Lung infection with organisms associated with a more rapid decline in pulmonary status (e.g., *Burkholderia cenocepacia*, *Burkholderia dolosa*, and *Mycobacterium abscessus*). For subjects who have had a history of a positive culture in the past, the investigator will apply the following criteria to establish whether the subject is free of infection with such organisms:
 - The subject has had 2 respiratory tract cultures negative for these organisms within the past 12 months, with no subsequent positive cultures.
 - These 2 respiratory tract cultures were separated by at least 3 months, and 1 of them was obtained within the past 6 months.
9. An acute illness not related to CF (e.g., gastroenteritis) within 14 days before the first dose of study drug (Day 1 for Part 1, Day -28 for Part 2).

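### A subject who passes the total-bilirubin exclusion can already meet the mandatory indirect-bilirubin interruption criterion before the first dose

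*Protocol*

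**What the plan says.** - **Entry.** In Protocol Section 9.2, criterion 6 is headed "Any of the following abnormal laboratory values at screening". Its only bilirubin line is "Total bilirubin $\geq 2 \times$ ULN". No other criterion caps indirect bilirubin; the exclusions for past haemolysis and for G6PD deficiency set no bilirubin value. SAP Appendix D repeats the criterion as E6, again for total bilirubin only.
- **Interruption.** Protocol Section 10.4 requires study drug to be interrupted "immediately (prior to confirmatory testing), and the medical monitor must be notified, if any of the following criteria are met". Three of the four criteria need a raised ALT or AST. The fourth is indirect bilirubin above 2 × ULN, that ULN being "defined as ULN for total bilirubin minus ULN for direct bilirubin".
- **Where the qualifier sits.** The close-follow-up paragraph at the start of Section 10.4 begins "Subjects with new treatment-emergent ALT or AST elevations of". The interruption sentence and its list contain no such condition and no reference to baseline.
- **Discontinuation.** The same indirect-bilirubin limit applies on confirmatory testing, but only "in association with decreased haptoglobin".
- **Resumption.** If a separate, reversible explanation has been found and the medical monitor approves, "study drug administration may be resumed once transaminases or bilirubin return to baseline or are" at or below 2 × ULN, the higher of the two applying. The bilirubin fraction is not named.
- **Scope.** Section 10 counts VX-661/IVA as study drug, so in Part 2 the rule is in force from the Run-in Period.

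**The concern.** An entry criterion and a mandatory interruption rule should fit together, so that a value accepted at screening does not by itself stop treatment. For the three transaminase-based criteria they do. For indirect bilirubin they do not: a subject can be correctly enrolled and, with nothing having changed, correctly interrupted.

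Either dosing is lost for a reason unrelated to treatment, or sites decide for themselves that a pre-existing value does not count and apply a mandatory safety rule unevenly. The treatment period is 2 weeks (4 in Cohort 2B) and the TC groups have 9 or 18 subjects, so one interrupted subject is a noticeable share of a group. In Part 2 the interruption would fall in the run-in, whose purpose is to establish the on-treatment baseline. Total and direct bilirubin are both scheduled on Days 1, 3, 5, 8, 11 and 15 (and on Day -28 in Part 2), so such a value would be seen.

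**Working it through.** The plan gives no figure to reproduce. The check compares two inequalities.

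**Inputs.** T and D are total and direct bilirubin; U_T and U_D are their ULNs. The rules come from Protocol Sections 9.2 and 10.4. The documents give no reference ranges, so U_D/U_T is assumed to lie between 0.10 and 0.40.

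**Step 1: the two rules.**
- Eligible: T < 2 U_T.
- Interrupt: T − D > 2 (U_T − U_D), which rearranges to T > 2 U_T − (2 U_D − D).

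**Step 2: where both hold.** Both are true when 2 U_T − (2 U_D − D) < T < 2 U_T. The width of this band is 2 U_D − D. It is non-empty whenever D < 2 U_D, for any U_D above zero. This step needs no assumed number.

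**Step 3: where the band starts.** Dividing by U_T, the lower edge is 2 − (2 U_D − D)/U_T. The upper edge is always 2.00 × U_T.

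| U_D/U_T (assumed) | D = 0.5 U_D | D = U_D | D = 1.5 U_D | D = 2 U_D |
|---|---|---|---|---|
| 0.10 | 1.85 | 1.90 | 1.95 | 2.00 (no band) |
| 0.20 | 1.70 | 1.80 | 1.90 | 2.00 (no band) |
| 0.25 | 1.625 | 1.75 | 1.875 | 2.00 (no band) |
| 0.30 | 1.55 | 1.70 | 1.85 | 2.00 (no band) |
| 0.40 | 1.40 | 1.60 | 1.80 | 2.00 (no band) |

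**Step 4: example, with assumed ULNs of 1.2 (total) and 0.3 (direct) mg/dL.**
- T = 2.3 is 2.3/1.2 = 1.92 × ULN, so the subject is eligible.
- With D = 0.3, indirect bilirubin is 2.0. The limit is 2 × (1.2 − 0.3) = 1.8, so interruption is mandatory.
- Counter-check: with D = 0.6 (2 × U_D), indirect bilirubin is 1.7, below 1.8, and the rule is not met.

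**Step 5: source of the overlap.** If indirect bilirubin were judged against U_T, no eligible subject could trigger the rule, because T − D ≤ T < 2 U_T. The overlap therefore comes from the smaller derived ULN, not from the change of fraction alone. The protocol's own definition rules out the U_T reading.

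**Step 6: the other criteria.** They need ALT or AST above 3, 5 or 8 × ULN, while criterion 6 excludes values of 3 × ULN or more. No eligible screening value can meet them.

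**Step 7: the way out for an unchanged value.** Discontinuation on this line also needs decreased haptoglobin, so a stable value without it is not discontinued. Taking baseline as the pre-dose value, the resumption level is already met: on the total fraction T < 2 U_T, and on the indirect fraction the value equals baseline, which is then the higher of the two references. Resumption still needs an identified reversible cause and approval, which a stable constitutional value may never supply.

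**The case against.** Section 10.4 opens with elevations that are new on treatment, and the interruption sentence refers back to confirmatory testing. A site could reasonably carry the qualifier forward and leave a pre-existing value alone. This is a fair reading, but it is an inference: the sentence that makes interruption mandatory does not say it.

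It is also true that this line leads to interruption and review, not to withdrawal by itself, and that before dosing only the numeric criterion is met; the interruption takes effect once dosing has begun.

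A reader might infer that bilirubin-related interruptions could no longer be read as a VX-152 signal. The documents do not support that:
- Protocol Section 13.1.1.2 ties laboratory AEs to worsening from baseline.
- Protocol Section 12.3.5.1 and SAP Section 8.5.1 require a TEAE to be new or worsened, and the SAP's count of interruptions is of those due to TEAEs. A stable value is not designed to enter it; it would appear as interruption days in compliance (SAP Section 8.2.5).
- SAP Section 8.5.2 plots maximum treatment-emergent against baseline total bilirubin, which would show a stable value as stable.
- Every cohort has a randomised comparator.
- In Part 2 a pre-existing value would trigger in the run-in, before VX-152 is given.

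A reader might also infer that some TC subject is likely to be affected. The documents give no prevalence, so any such probability would only restate an assumed input.

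**Conclusion.** The point holds as a mismatch between two stated rules. For every subject with direct bilirubin below 2 × its ULN, there is a range of total bilirubin that is eligible under Section 9.2 and already meets the mandatory interruption criterion of Section 10.4. The existence of the range follows from the protocol's wording alone. Its position depends on assumed reference ranges: with direct bilirubin at its ULN, it starts at 1.90 × ULN of total bilirubin for a direct-to-total ULN ratio of 0.10 and at 1.60 × ULN for a ratio of 0.40.

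The consequence is avoidable loss of dosing or uneven use of a mandatory rule, with no clear exit for an unchanged value. How many subjects would be affected cannot be estimated from the documents. The point should be settled because safety is the primary objective and clarification is cheap; it does not undermine the safety analysis as a whole.

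**What to change.** The sponsor should reconcile criterion 6 of Protocol Section 9.2 with the indirect-bilirubin line of Section 10.4. The reconciled text should state how Section 10.4, including its interruption and resumption provisions, treats a bilirubin value already present before the first dose (Day 1 in Part 1, Day -28 in Part 2). Any change to criterion 6 should be carried into item E6 of SAP Appendix D. Which limit applies and what form the rule takes are for the sponsor's safety group; none is proposed here.

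The cost is one or two sentences in the protocol and, if criterion 6 changes, the matching SAP line. No new test is needed, since both fractions are already measured. Depending on how the passages are reconciled, there may be an occasional extra screen failure.

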10.5 Packaging and Labeling

Study drug tablets will be supplied in blister cards by Vertex. Study drug labeling will be in compliance with applicable local and national regulations. Additional details regarding packaging, labeling, and dispensing for study drug will be included in the Pharmacy Manual.

10.6 Study Drug Supply, Storage, and Handling

VX-152 (100 mg) and matching placebo will be supplied as tablets of similar size and appearance containing 100 mg VX-152 and 0 mg VX-152, respectively.

VX-661/IVA (100 mg/150 mg) and matching placebo will be supplied as light yellow film-coated tablets of similar size and appearance containing 100 mg VX-661/150 mg IVA and 0 mg VX-661/0 mg IVA, respectively.

IVA (150 mg) and matching placebo will be supplied as light blue film-coated tablets of similar size and appearance containing 150 mg IVA and 0 mg IVA, respectively.

Blister cards must be stored under conditions noted in Table 10-1 and in the Pharmacy Manual. The investigator, or an authorized designee (e.g., a licensed pharmacist), will ensure that all investigational product is stored in a secured area, under recommended storage conditions, and in accordance with applicable regulatory requirements. To ensure adequate records, all study drugs will be accounted for via the drug accountability forms as instructed by Vertex.

Table 10-1 Study Drug

Drug Name	Strength/Formulation/ Route	Dosage	Storage Condition
VX-152	100-mg tablet, oral	100, 200, or 300 mg q12h (planned)	≤25°C (77°F) with excursions to 30°C (86°F)
VX-152-matching placebo	0-mg tablet, oral	0 mg q12h	≤25°C (77°F) with excursions to 30°C (86°F)
VX-661/IVA fixed-dose	100-mg/150-mg tablet; oral	100 mg/150 mg qd (morning dose)	≤25°C (77°F) with excursions to 30°C (86°F)
VX-661/IVA-matching placebo	0-mg/0-mg tablet; oral	0 mg/0 mg qd (morning dose)	≤25°C (77°F) with excursions to 30°C (86°F)
IVA	150-mg tablet, oral	150 mg qd (evening dose) 150 mg q12h	≤25°C (77°F) with excursions to 30°C (86°F)
IVA-matching placebo	0-mg tablet, oral	0 mg qd (evening dose) 0 mg q12h	≤25°C (77°F) with excursions to 30°C (86°F)

